7.1.2 Disease Parameters

Measurable disease. Measurable lesions are defined as those that can be accurately measured in at least one dimension (longest diameter to be recorded) as ≥ 20 mm by chest x-ray, as ≥ 10 mm with CT scan, or ≥ 10 mm with calipers by clinical exam. All tumor measurements must be recorded in millimeters (or decimal fractions of centimeters).

Note: Tumor lesions that are situated in a previously irradiated area might or might not be considered measurable. Tumors within a previously

irradiated field will be designated as “non-target” lesions, unless progression is documented or a biopsy is obtained to confirm persistence at least 90 days following completion of radiation therapy.

Malignant lymph nodes. To be considered pathologically enlarged and measurable, a lymph node must be ≥ 15 mm in short axis when assessed by CT scan (CT scan slice thickness recommended to be no greater than 5 mm). At baseline and in follow-up, only the short axis will be measured and followed.

Non-measurable disease. All other lesions (or sites of disease), including small lesions (longest diameter < 10 mm or pathological lymph nodes with ≥ 10 to < 15 mm short axis), are considered non-measurable disease. Bone lesions, leptomeningeal disease, ascites, pleural/pericardial effusions, lymphangitis cutis/pulmonitis, inflammatory breast disease, and abdominal masses (not followed by CT or MRI), are considered as non-measurable.

Note: Cystic lesions that meet the criteria for radiographically defined simple cysts should not be considered as malignant lesions (neither measurable nor non-measurable) since they are, by definition, simple cysts.

‘Cystic lesions’ thought to represent cystic metastases can be considered as measurable lesions, if they meet the definition of measurability described above. However, if non-cystic lesions are present in the same patient, these are preferred for selection as target lesions.

Target lesions. All measurable lesions up to a maximum of 2 lesions per organ and 5 lesions in total, representative of all involved organs, should be identified as **target lesions** and recorded and measured at baseline. Target lesions should be selected on the basis of their size (lesions with the longest diameter), be representative of all involved organs, but in addition should be those that lend themselves to reproducible repeated measurements. It may be the case that, on occasion, the largest lesion does not lend itself to reproducible measurement in which circumstance the next largest lesion which can be measured reproducibly should be selected. A sum of the diameters (longest for non-nodal lesions, short axis for nodal lesions) for all target lesions will be calculated and reported as the baseline sum diameters. If lymph nodes are to be included in the sum, then only the short axis is added into the sum. The baseline sum diameters will be used as reference to further characterize any objective tumor regression in the measurable dimension of the disease.

Non-target lesions. All other lesions (or sites of disease) including any measurable lesions over and above the 5 target lesions should be

identified as **non-target lesions** and should also be recorded at baseline. Measurements of these lesions are not required, but the presence, absence, or in rare cases unequivocal progression of each should be noted throughout follow-up.

7.1.3 Methods for Evaluation of Measurable Disease

All measurements should be taken and recorded in metric notation using a ruler or calipers. All baseline evaluations should be performed as closely as possible to the beginning of treatment and never more than 4 weeks before the beginning of the treatment.

The same method of assessment and the same technique should be used to characterize each identified and reported lesion at baseline and during follow-up. Imaging-based evaluation is preferred to evaluation by clinical examination unless the lesion(s) being followed cannot be imaged but are assessable by clinical exam.

Clinical lesions Clinical lesions will only be considered measurable when they are superficial (e.g., skin nodules and palpable lymph nodes) and ≥ 10 mm diameter as assessed using calipers (e.g., skin nodules). In the case of skin lesions, documentation by color photography, including a ruler to estimate the size of the lesion, is recommended.

Chest x-ray Lesions on chest x-ray are acceptable as measurable lesions when they are clearly defined and surrounded by aerated lung. However, CT is preferable.

Conventional CT and MRI This guideline has defined measurability of lesions on CT scan based on the assumption that CT slice thickness is 5 mm or less. If CT scans have slice thickness greater than 5 mm, the minimum size for a measurable lesion should be twice the slice thickness. MRI is also acceptable in certain situations (e.g. for body scans).

Use of MRI remains a complex issue. MRI has excellent contrast, spatial, and temporal resolution; however, there are many image acquisition variables involved in MRI, which greatly impact image quality, lesion conspicuity, and measurement. Furthermore, the availability of MRI is variable globally. As with CT, if an MRI is performed, the technical specifications of the scanning sequences used should be optimized for the evaluation of the type and site of disease. Furthermore, as with CT, the modality used at follow-up should be the same as was used at baseline and the lesions should be measured/assessed on the same pulse sequence. It is beyond the scope of the RECIST guidelines to prescribe specific MRI pulse sequence parameters for all scanners, body parts, and

diseases. Ideally, the same type of scanner should be used and the image acquisition protocol should be followed as closely as possible to prior scans. Body scans should be performed with breath-hold scanning techniques, if possible.

7.1.4 Response Criteria

7.1.4.1 Evaluation of Target Lesions

Complete Response (CR): Disappearance of all target lesions. Any pathological lymph nodes (whether target or non-target) must have reduction in short axis to <10 mm.

Partial Response (PR): At least a 30% decrease in the sum of the diameters of target lesions, taking as reference the baseline sum diameters

Progressive Disease (PD): At least a 20% increase in the sum of the diameters of target lesions, taking as reference the smallest sum on study (this includes the baseline sum if that is the smallest on study). In addition to the relative increase of 20%, the sum must also demonstrate an absolute increase of at least 5 mm. (Note: the appearance of one or more new lesions is also considered progressions).

Stable Disease (SD): Neither sufficient shrinkage to qualify for PR nor sufficient increase to qualify for PD, taking as reference the smallest sum diameters while on study

7.1.4.2 Evaluation of Non-Target Lesions

Complete Response (CR): Disappearance of all non-target lesions and normalization of tumor marker level. All lymph nodes must be non-pathological in size (<10 mm short axis)

Note: If tumor markers are initially above the upper normal limit, they must normalize for a patient to be considered in complete clinical response.

Non-CR/Non-PD: Persistence of one or more non-target lesion(s) and/or maintenance of tumor marker level above the normal limits

Progressive Disease (PD): Appearance of one or more new lesions and/or *unequivocal progression* of existing non-target lesions. *Unequivocal progression* should not normally trump target lesion status. It must be representative of overall disease status change, not a single lesion increase.

Although a clear progression of “non-target” lesions only is exceptional, the opinion of the treating physician should prevail in such circumstances, and the progression status should be confirmed at a later time by the review panel (or Principal Investigator).

7.1.4.3 Evaluation of Best Overall Response

The best overall response is the best response recorded from the start of the treatment until disease progression/recurrence (taking as reference for progressive disease the smallest measurements recorded since the treatment started). The patient's best response assignment will depend on the achievement of both measurement and confirmation criteria.

For Patients with Measurable Disease (i.e., Target Disease)

Target Lesions	Non-Target Lesions	New Lesions	Overall Response	Best Overall Response when Confirmation is Required*
CR	CR	No	CR	≥4 wks. Confirmation**
CR	Non-CR/Non-PD	No	PR	≥4 wks. Confirmation**
CR	Not evaluated	No	PR	
PR	Non-CR/Non-PD/not evaluated	No	PR	
SD	Non-CR/Non-PD/not evaluated	No	SD	documented at least once ≥4 wks. from baseline**
PD	Any	Yes or No	PD	no prior SD, PR or CR
Any	PD***	Yes or No	PD	
Any	Any	Yes	PD	

* See RECIST 1.1 manuscript for further details on what is evidence of a new lesion.

** Only for non-randomized trials with response as primary endpoint.

*** In exceptional circumstances, unequivocal progression in non-target lesions may be accepted as disease progression.

Note: Patients with a global deterioration of health status requiring discontinuation of treatment without objective evidence of disease progression at that time should be reported as “*symptomatic deterioration*.” Every effort should be made to document the objective progression even after discontinuation of treatment.

For Patients with Non-Measurable Disease (i.e., Non-Target Disease)

Non-Target Lesions	New Lesions	Overall Response
CR	No	CR
Non-CR/non-PD	No	Non-CR/non-PD*
Not all evaluated	No	not evaluated
Unequivocal PD	Yes or No	PD
Any	Yes	PD

* ‘Non-CR/non-PD’ is preferred over ‘stable disease’ for non-target disease since SD is increasingly used as an endpoint for assessment of efficacy in some trials so to assign this category when no lesions can be measured is not advised

7.1.5 Duration of Response

Duration of overall response: The duration of overall response is measured from the time measurement criteria are met for CR or PR (whichever is first recorded) until the first date that recurrent or progressive disease is objectively documented (taking as reference for progressive disease the smallest measurements recorded since the treatment started).

The duration of overall CR is measured from the time measurement criteria are first met for CR until the first date that progressive disease is objectively documented.

Duration of stable disease: Stable disease is measured from the start of the treatment until the criteria for progression are met, taking as reference the smallest measurements recorded since the treatment started, including the baseline measurements.

Patients achieving a complete response, once confirmed, are permitted to stop study medication. Subsequent follow-up will be at the discretion of the treating physician.

7.1.6 Other efficacy parameters

Duration of disease control, time to disease progression, and survival will be evaluated.

7.1.7 Safety assessments

Safety assessments will consist of monitoring and recording all adverse events and serious adverse events, the regular monitoring of hematology, blood chemistry and urine values, regular measurement of vital signs and the performance of physical examinations.

7.1.7.1 Adverse events

Adverse events will be recorded and collected in the in accordance with the Adverse Event Recording Guidelines (Described in the Data Quality Management Plan (DQMP) Appendix L.

8 STUDY MONITORING

Study Monitoring procedures are described in the Data Quality Management Plan (DQMP) Appendix L.

9 DATA MANAGEMENT

9.1 **Registration**: MDACC will serve as the primary site for this study. All patients enrolled in the study from each of the participating sites will be registered in the Clinical Oncology Research System (CORe) at MDACC following procedures described in section 5.1. Patient data will be collected and entered in the MDACC's Protocol Data Monitoring System (PDMS).

9.2 **Confidentiality Procedures**: All pathology specimens, evaluations forms, reports and other records will be identified in a manner designed to maintain patient confidentiality. All records will be kept in a secure storage area with limited access. Clinical information will not be released without the written permission of the patient or the patient's guardian, except as necessary for monitoring by the OMCR or its representative, regulatory authorities, or the IRB.

The investigators and all employees and co-workers involved with this study shall not disclose or use for any purpose, other than performance of the study, any data, records or other unpublished, confidential information disclosed to those individuals for the purpose of the study. No patient identifiers will be used when analyzing the data or reporting the results.

9.3 **Data Safety and Monitoring Committee**: The MDACC Data Safety and Monitoring Committee will monitor the overall conduct of the study.

10 STATISTICAL METHODOLOGY

This is a phase II activity trial. We will accrue a minimum of 10 patients and a maximum of 35 evaluable patients at a rate of 2 patients per month. We estimate 7 patients will be inevaluable and thus need to be replaced. Therefore our total number of patients will not exceed 42. The primary outcome for this trial is the objective response or stable disease rate (CR + PR + SD), which is evaluated within approximately 8 weeks of treatment. A confirmatory evaluation will be made no sooner than 4 weeks from this event (8 weeks, if SD). Once a response category is confirmed, evaluation for objective responses will be made every 12 weeks as outlined in Sections 6 and 7.1.3. Our target objective response or stable disease rate is 20%. We will monitor the objective response or stable disease rate as patients accrue and are evaluated following the example of Thall and Simon.[17] We will stop the trial if we have evidence that the target objective response or stable disease rate cannot be met.

We will stop the trial early if $P(\text{objective response or stable disease rate} \geq 20\% \mid \text{data from the trial}) < 0.10$. That is, given the outcomes from the patients who have already been evaluated, if we determine that there is less than a 10% chance that the objective response or stable disease rate is 20% or more, we will stop the trial. This decision rule gives the following stopping rule. We assume a uniform prior distribution for the rate of objective response or stable disease. Stop the trial if: $[\# \text{ of patients with objective response or stable disease} / \# \text{ of patients evaluated}] < 1/10, 2/17, 3/24, 4/31$.

The operating characteristics of this study design are shown in the following table.

Operating Characteristics of Monitoring Rule				
Rate of CR + PR + SD	Probability of Stopping Early	P ₂₅	P ₅₀	P ₇₅
0.05	0.956	10	10	17
0.10	0.725	10	17	35
0.15	0.436	17	35	35
0.20	0.220	35	35	35
0.25	0.097	35	35	35

We will estimate the rate OF CR + PR + SD with a 90% credible interval once the study is complete. If we complete the study with 11 patients with treatment success (CR or PR or SD) among 35 patients total (31%), then our 90% credible interval for the success rate would be 20.5 to 45.5%.

We will also estimate the overall survival and progression free survival for patients on study with the product-limit estimator of Kaplan and Meier (1958). [18]

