1.7.3 Combination Phase 1b study

An ongoing interaction study (Protocol CRAD001C2108) investigates the combination of letrozole (2.5mg/d) with RAD001 at escalating doses in patients receiving letrozole as first-line therapy for advanced HR+ breast cancer. To be eligible, patients have to have received letrozole already for a minimum of 4 months with sub optimal response, defined as: stable disease or progressive disease without urgent indication to go to chemotherapy (e.g. bulky or symptomatic disease). All patients continue to receive letrozole 2.5 mg once daily, to which RAD001 is added. Successive cohorts are defined by the dosage of RAD001: 5mg and then 10mg/d. Assessed over the first 28 days of the combined therapy, DLT is defined as any grade 3-4 toxicity with the exception of grade 3 hypercholesterolemia, hypertriglyceridemia, or lymphopenia as well as any toxicity requiring interruption of treatment for more than two weeks.

The main safety events are summarized in Table 1-5. One patient (RAD001 at 10mg/d) has been reported with a DLT, this being a grade 3 thrombocytopenia, the nadir ($48 \times 10^9/L$) of a progressive decline in the platelet count over 3 weeks treatment. Recovery followed interruption of treatment. No other DLT or grade 3-4 adverse events have been reported. Suspected ADRs occurring in more than 10% of patients (i.e. $\geq 2/11$ patients documented so far) include: fatigue/asthenia (n=8), stomatitis/mucositis (n=5), headache, rash/skin reaction (n=3 each), diarrhea, nausea (n=2 each). A patient with coexisting chronic viral hepatitis was discontinued when her serum transaminase activity increased from grade 1 to grade 2.

Table 1-5. Study 2108 (RAD001 + letrozole) Main safety events (July 04)

Letrozole 2.5 mg/d + RAD 001	RAD001 5 mg/day N=6	RAD001 10mg/day N=9
DLT	0/6	1/9
Pts with Gr 3/4 suspected ADR	0	1 ²
Discontinuations / Death	0	0
Progressive disease	2	2
Adverse events	1 ¹	1
Withdrew consent	0	0
Suspected drug-related SAEs	0	1 ³

DLT: dose-limiting toxicity in first 4 weeks (# of pts with DLT/mo of those evaluable for DLT)

ADR: adverse drug reaction

SAE: serious adverse event (death or potentially fatal; requiring or prolonging hospitalization)

1. discontinuation for raised serum transaminase activity (patient with chronic viral hepatitis)
2. grade 3 thrombocytopenia
3. hospitalization of the patient who developed grade 3 thrombocytopenia

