3 INVESTIGATIONAL PLAN

This is a phase II activity trial of RAD001 in combination with letrozole for patients with recurrent or progressive endometrial cancer. We will enroll a minimum of 10 patients and a maximum of 35 patients. Patients will be enrolled at M.D. Anderson Cancer Center and at Morristown Memorial Hospital, Women's Cancer Center. Our goal is to obtain a response rate or stable disease rate of greater than 20 % in patients with recurrent or progressive endometrial cancer. For the purposes of this study, response rate will be defined as stable disease, partial response or complete response. Early stopping points have been incorporated to stop the trial if there is limited disease control. We will also evaluate the toxicity profile of letrozole and RAD001 in this cohort of patients with endometrial cancer. Patients will be evaluated for response rate, duration of response rate, time to disease progression, and survival.

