10.1 Definition of Populations for Analyses

Patients who are removed from the study during the first course because of progression are considered evaluable for efficacy only if progression can be documented per RECIST 1.1 criteria. Patients who come off

treatment for reasons other than progression (and prior to establishing response) are evaluable for toxicity only.

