10.3 Safety Analyses

All eligible patients who receive therapy on this study will be considered evaluable for safety. Patients who are removed from the study during the first course because of progression, serious drug related adverse events, or for other reasons (e.g. patient request or non-drug related toxicity) will also be evaluable for safety.

Descriptive statistics and tabulations will be used to summarize adverse events and laboratory data. Transition tables will be used to describe changes in laboratory values from baseline to follow-up.

11 Special safety-related procedures

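### The supplied text sets no trial-level toxicity criterion, and the one numerical stopping rule cannot respond to toxicity that removes patients before response is established

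*Combined protocol and SAP*

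**What the plan says.** **Stopping rule.** Section 3 gives the purpose of the interim looks: "Early stopping points have been incorporated to stop the trial if there is limited disease control". Section 10 makes this operational with a uniform prior. The trial stops "if we determine that there is less than a 10% chance that the objective response or stable disease rate is 20% or more", which gives bounds of fewer than 1/10, 2/17, 3/24 or 4/31 successes among evaluated patients. The consequence is stated as "We will stop the trial if we have evidence that the target objective response or stable disease rate cannot be met". A success is CR, PR or SD.

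**Who is counted.** Under Section 10.1, patients who come off "treatment for reasons other than progression (and prior to establishing response) are evaluable for toxicity only". Section 10 allows for 7 inevaluable patients to be replaced, with a maximum of 35 evaluable and 42 in total.

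**Safety.** Toxicity is a secondary objective (2.2.2). Section 10.3 plans the analysis as follows: "Descriptive statistics and tabulations will be used to summarize adverse events and laboratory data". Section 5.3 has removal criteria, but they act on one patient at a time.

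**Oversight.** Section 9.3 says: "The MDACC Data Safety and Monitoring Committee will monitor the overall conduct of the study". Section 4.4 foresees termination by the investigator or sponsor. Section 11.1 requires SAE reports to the IRB and the manufacturer. Sections 7.1.7.1, 8 and 11.1 refer adverse event recording, study monitoring and SAE reporting to the Data Quality Management Plan, Appendix L.

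**The concern.** A futility rule on disease control can sometimes act as an indirect brake on a poorly tolerated regimen, because patients who cannot stay on treatment count as failures. Section 10.1 removes that effect here. A patient who leaves for toxicity before response is established is in neither the numerator nor the denominator of the monitored fraction, and is replaced. The rule sees only patients who tolerated treatment long enough to be assessed. If enough of them are stable, no stated number of toxicity removals calls for a review.

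The combination data at the starting dose are few. Section 1.7.3 describes breast-cancer patients already on letrozole for at least 4 months, 9 of them at RAD001 10 mg/day: "One patient (RAD001 at 10mg/d) has been reported with a DLT, this being a grade 3 thrombocytopenia". What is at stake is how many patients are exposed before anyone is required to ask whether the regimen is tolerable in this population.

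**Working it through.** **1. Reproduce the plan's rule.** With a uniform prior and x successes in n, the posterior is Beta(1+x, 1+n−x). P(rate ≥ 20%) is 0.086 at 0/10 (that is, 0.8^11), 0.099 at 1/17, 0.098 at 2/24 and 0.093 at 3/31. Each is the first n at which that x falls below 0.10, so the printed bounds are confirmed.

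Exact binomial recursion, maximum 35 evaluable:

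| True CR+PR+SD rate | Plan | Recomputed |
|---|---|---|
| 0.05 | 0.956 | 0.955 |
| 0.10 | 0.725 | 0.723 |
| 0.15 | 0.436 | 0.432 |
| 0.20 | 0.220 | 0.220 |
| 0.25 | 0.097 | 0.101 |

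**2. Add early toxicity removal.** Each enrolled patient leaves for toxicity before response is established with probability q and is dropped, as in 10.1. The others succeed with probability p. Enrolment ends at 35 evaluable or 42 in total. The documents give no q, so a range is shown. For p, Section 1.5 reports 12/28 = 43% in the single-agent RAD001 trial. The 20% target is shown beside it.

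| q | P(stop), p = 0.43 | P(stop), p = 0.20 |
|---|---|---|
| 0 | 0.0043 | 0.220 |
| 0.3 | 0.0042 | 0.205 |
| 0.5 | 0.0041 | 0.167 |
| 0.7 | 0.0031 | 0.097 |
| 1.0 | 0 | 0 |

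The probability never rises with q. It falls because fewer patients reach the looks. At q = 1 nobody is evaluable, so the look at 10 never occurs. With p = 0.43, expected enrolment is about 41.9 at q = 0.3 and at q = 0.5. Expected toxicity removals are then 41.9 × 0.3 = 12.6 and 41.9 × 0.5 = 21.0.

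**3. What the combination data allow.** One DLT in 9 with a uniform prior gives Beta(2, 9), with a 90% credible interval of 3.7% to 39.4%. This is for 28-day DLT in another disease, so it shows only how little 9 patients can exclude.

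**4. Counting removals as failures would not be enough.** With removals kept in the existing rule as non-successes and p = 0.43, P(stop) is 0.043 at q = 0.3, 0.18 at 0.5 and 0.55 at 0.7.

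**5. Illustration of a separate rule.** Assume a pause if P(event rate > 30% | data) > 0.90, a uniform prior, looks at 10, 17, 24 and 31 treated, maximum 42, and outcomes known at each look. The posterior is Beta(1+t, 1+n−t) for t events. The bounds are at least 5/10, 8/17, 10/24 and 13/31.

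| True event rate | P(pause) | Expected treated |
|---|---|---|
| 0.10 | 0.002 | 41.9 |
| 0.20 | 0.04 | 40.7 |
| 0.30 (the ceiling) | 0.25 | 35.2 |
| 0.40 | 0.64 | 25.0 |
| 0.50 | 0.92 | 16.1 |

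Expected treated counts a pause as the end of accrual. Outcomes will in practice arrive late. At 2 patients per month (Section 10), an assumed lag of 2 to 4 months adds 4 to 8 patients after each look. Expected treated then becomes about 28 to 30 at a 40% rate and 20 to 23 at 50%.

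The result depends on the ceiling. At 25%, the pause probabilities at true rates of 20%, 40% and 50% are 0.08, 0.81 and 0.975. At 33% they are 0.01, 0.45 and 0.83.

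**The case against.** A reader might infer that no level of toxicity can pause this trial. The documents do not support that. A Data Safety and Monitoring Committee oversees the study, the investigator or sponsor may terminate it, and serious events go to the IRB and, within 24 hours, to the manufacturer whether or not they are thought drug related. Appendix L was not among the documents reviewed and may hold a trial-level criterion. What can be said is that none appears in the supplied text.

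Three other strong readings also fail:

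- Not every toxicity removal is dropped. Section 10.1 excludes only those before response is established, so a patient with established disease control who stops later still counts as a success.
- Replacement is not open-ended. Seven are planned and 42 is the limit, so further removals shrink the evaluable sample.
- The futility rule can still end the trial early for low disease control.

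The safety background is also wider than 9 patients. In the phase III renal trial (274 on everolimus), 7% discontinued permanently for adverse reactions (Section 1.4.4.2). Section 1.5 reports 35 women with endometrial cancer on single-agent RAD001 and describes side effects as not problematic. Section 1.7.3 reports no sign of a pharmacokinetic interaction. If the true event rate is near 7%, a toxicity rule would almost never act. Against this, 17 of those 35 women needed dose reduction, and Section 5.3 here has one reduced level before off study, so removals are foreseeable.

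These points narrow the claim but do not remove it. Discretionary powers have no stated trigger and no operating characteristics.

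**Conclusion.** The point holds in this form: the supplied text has no pre-specified trial-level toxicity criterion, and the only numerical rule cannot respond to toxicity that removes patients before response is established. At 43% disease control among evaluable patients it stops with probability about 0.004 for early removal rates up to 50%, and less beyond that. At the 20% target, a 50% removal rate lowers the stopping probability from 0.220 to 0.167.

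This rests on Section 10.1 being applied as written, on removal being independent of disease control in those who remain, and on Appendix L containing no such boundary, which could not be checked. The 43% is borrowed from a single-agent trial. The change should be made. It is a gap in the design, not an error in the plan's arithmetic, which reproduces.

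**What to change.** Add to Section 10 a second Bayesian rule, run in parallel with the futility rule at the existing look sizes (10, 17, 24 and 31), but counted over all treated patients, including those whom 10.1 calls evaluable for toxicity only. The sponsor defines the event, its time window, the ceiling and the probability cut-off. Crossing the bound pauses accrual for review by the existing Data Safety and Monitoring Committee, and Section 9.3 should name that trigger.

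The window matters because many removals under Section 5.3 need a repeat event or a long interruption and may come months after the start. Print the operating characteristics beside the present table, including the row at the ceiling itself, and allow for the lag in outcomes. If Appendix L already holds such a boundary, a citation in Section 10 is enough.

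The cost is protocol wording and one table, with no new committee or visits, and no new data if the event is one already recorded, such as removal for toxicity. The downside is an occasional unnecessary pause, about 4% at a true 20% rate under the illustrative 30% ceiling. A pause leads to review and does not by itself end the trial.
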